8.1.5 Reporting of Serious Adverse Events

All SAEs (as defined below), regardless of treatment group or suspected relationship to triptorelin, must be reported immediately (within 24 hours of the Investigator's knowledge of the event) using the SAE report form via the email address or the fax number specified at the beginning of this protocol as well as recording them in the eCRF.

An SAE is defined as any untoward medical occurrence that, at any dose, meets one or more of the criteria listed:

- (1) Results in death

(2) Is life threatening. The term ‘life-threatening’ in the definition of ‘serious’ refers to an event in which the participant was at risk of death at the time of the event. It does not refer to an event, which hypothetically might have caused death, if it were more severe

(3) Requires in-patient hospitalisation or prolongation of existing hospitalisation.

In general, hospitalisation signifies that the participant has been admitted (usually involving at least an overnight stay) at the hospital or emergency ward for observation and/or treatment that would not have been appropriate in the physician’s office or outpatient setting. Complications that occur during hospitalisation are AEs. If a complication prolongs hospitalisation or fulfils any other serious criteria, the event is serious. When in doubt as to whether “hospitalisation” occurred or was necessary, the AE should be considered serious.

Hospitalisation for elective treatment of a pre-existing condition that did not worsen from baseline is not considered an AE

(4) Results in a persistent or significant disability/incapacity. The term disability means a substantial disruption of a person’s ability to conduct normal life functions.

This definition is not intended to include experiences of relatively minor medical significance such as uncomplicated headache, nausea, vomiting, diarrhoea, influenza and accidental trauma (e.g. sprained ankle) that may interfere with or prevent everyday life functions but do not constitute a substantial disruption.

(5) Results in congenital anomaly/birth defect in the offspring of a participant who received the triptorelin

(6) Is an important medical event that may not result in death, be life threatening, or require hospitalisation but, based upon appropriate medical judgement, may jeopardise the participant and may require medical or surgical intervention to prevent one of the outcomes listed in this definition. Examples of such medical events include allergic bronchospasm requiring intensive treatment in an emergency room or at home, blood dyscrasias or convulsions that do not result in in-patient hospitalisation, or the development of drug dependency or drug abuse.

Medical or scientific judgment should be exercised by the Investigator in deciding whether SAE reporting is appropriate in other situations such as significant medical events that may jeopardise the participant or may require medical or surgical intervention to prevent one of the other outcomes listed in the above definition. These events should usually be considered serious.

Examples of such events include invasive or malignant cancers, intensive treatment for allergic bronchospasm, blood dyscrasias, convulsions or development of intervention dependency or intervention abuse.

A suspected or confirmed coronavirus COVID-19 (SARS-CoV-2) infection must be reported as serious (seriousness criteria should be “other medically significant” if no other seriousness criteria are present (e.g. hospitalisation).

- **Hospitalisation** is defined as any in-patient admission (even if less than 24 hours). For chronic or long-term in-patients, in-patient admission also includes transfer within the hospital to an acute/intensive care in-patient unit
- **Prolongation of hospitalisation** is defined as any extension of an in-patient hospitalisation beyond the stay anticipated/required for the reason for the initial admission, as determined by the Investigator or treating physician. For protocol-specified hospitalisation in clinical studies, prolongation is defined as any extension beyond the length of stay described in the protocol. Prolongation in the absence

of a precipitating, TEAEs (i.e. not associated with the development of a new AE or worsening of a pre-existing condition) may meet the criteria for "seriousness" but is not an adverse experience and thus is not subject to immediate reporting to the Sponsor

- Preplanned or elective treatments/surgical procedures should be noted in the participant's screening documentation. Hospitalisation for a preplanned or elective treatment/surgical procedure should not be reported as an SAE unless there are complications or sequelae that meet the criteria for seriousness described above.

Any SAE must be reported immediately (within 24 hours), using the SAE report form via the email address or the fax number specified at the beginning of this protocol as well as recording them in the eCRF, independent of the circumstances or suspected cause, if it occurs or comes to the attention of the Investigator at any time during the study period.

Any AE/SAE with a suspected causal relationship to triptorelin administration occurring at any other time after completion of the study must be reported promptly, within 24 hours.

The following information is the minimum that must be provided to the Sponsor within 24 hours for each SAE:

- Study number
- Centre number
- Participant number
- AE
- Investigator's name and contact details.

The additional information included in the SAE form must be provided to the Sponsor or representative as soon as it is available. The Investigator should always provide an assessment of causality for each event reported to the Sponsor. Upon receipt of the initial report, the Sponsor will ask for the Investigator's causality assessment if it was not provided with the initial report.

The Investigator should report a diagnosis or a syndrome rather than individual signs or symptoms. The Investigator should also try to separate a primary AE considered the foremost untoward medical occurrence from secondary AEs that occurred as complications.

8.1.6 *Pregnancy*

Information regarding pregnancies must be collected as an SAE on the AE page of the eCRF and reported to the Sponsor within 24 hours as described in Section 8.1.5.

If pregnancy occurs during the study, the outcome of the pregnancy will be collected following completion of the study. The Sponsor will request further information from the Investigator as to the course and outcome of the pregnancy using the Standard Drug Exposure for Pregnancy Form.

The Investigator must instruct all female participants who have already had menophaenia/menarche to inform them immediately should they become pregnant during the study. The Investigator should counsel the participant, discuss the risks of continuing with the pregnancy and the possible effects on the foetus. Monitoring of the participant should continue until conclusion of the pregnancy, which may involve follow-up after the participant's involvement in the study has ended.

Pregnancies with a conception date within 3 months after the participant's last dose of study medication must also be reported to the Investigator for onward reporting to the Sponsor.

If the Investigator becomes aware of a pregnancy occurring in the partner of a participant participating in the study, this should be reported to the Sponsor as described above. Pregnancies in the partner with a conception date until 3 months after participant's last dose of

study medication should be reported after the partner has given written consent and the partner should be counselled and followed as described above. Monitoring of the partner should continue until conclusion of the pregnancy.

8.1.7 *Deaths*

All AEs resulting in death during the study period (from first injection until 3 months after the date of the last study drug administration), must be reported as an SAE within 24 hours of the Investigator's knowledge of the event.

The convention for recording death is as follows:

- AE term: lead cause of death (e.g. multiple organ failure, pneumonia, myocardial infarction)
- Outcome: fatal.

The **only exception** is if the cause of death is unknown (i.e. sudden or unexplained death), in which case the AE term may be reported as "death" or "sudden death".

8.1.8 *Discontinuation/Withdrawal due to Adverse Events/Serious Adverse Events*

Discontinuation/withdrawal due to AEs should be distinguished from discontinuation/withdrawal due to insufficient response to triptorelin (see Section 4.4).

If triptorelin is discontinued due to an SAE, it must be reported immediately to the Sponsor's designated representative (see Section 8.1.5).

In all cases, the Investigator must ensure that the participant receives appropriate medical follow-up (see Section 8.1.4).

8.1.9 *Reporting to Competent Authorities/Independent Ethics Committees/Institutional Review Boards/Other Investigators*

The Sponsor will ensure that processes are in place for the submission of reports of suspected unexpected serious adverse reactions (SUSARs) occurring during the study to the competent authorities, IECs and other Investigators involved with triptorelin. Reporting will be in accordance with the applicable regulatory requirements.

8.2 Clinical Laboratory Tests

Blood and urine samples will be collected as per Table 1 and Table 2 for the evaluation of haematology, serum chemistry and urinalysis.

The Investigator will review the safety laboratory test results, document the review and record any clinically relevant changes occurring or observed during the study in the AE section of the eCRF (see Section 8.1.2.4 for abnormal laboratory tests that should be recorded as AEs).

All clinically relevant abnormal laboratory tests occurring during the study will be repeated at appropriate intervals until they return to baseline or to a level deemed acceptable by the Investigator and the Sponsor's clinical monitor (or his/her designated representative) or until the abnormality is explained by an appropriate diagnosis.

8.2.1 *Haematology*

Blood samples (volume to be collected as per local laboratory manual) will be collected in a potassium ethylenediaminetetraacetic acid tube to assess CBC.

8.2.2 *Blood Chemistry*

Blood samples (volume collected as per local clinical practice) will be collected in an activator gel tube to assess the following parameters:

- Creatinine

- Glucose
- ALT
- AST
- ALP
- Bilirubin.

In the case of abnormal blood glucose as per Investigator's judgement, repetition of these tests will be performed before the first triptorelin injection.

8.2.3 *Urinalysis*

Fresh urine samples (at least 10 mL) will be collected to assess the following variables: pH, protein, ketones, bilirubin, blood, urobilinogen, nitrites, leukocytes, glucose and specific gravity by dipstick.

Microscopy will be performed, if indicated, but results will not be collected in the eCRF. If in the opinion of the Investigator there are any clinically significant abnormalities in microscopy, they will be recorded as an AE in the eCRF.

8.2.4 *Pregnancy Test*

Local urine testing will be standard for the protocol unless serum testing is required by local regulation or IRB/IEC before drug treatment for all female participants of childbearing potential and if clinically indicated thereafter. Any participant becoming pregnant during the study will be withdrawn. All pregnancies that occur during the study are to be reported as described in Section 8.1.6.

8.2.5 *Other Clinical Laboratory Tests*

Other clinical laboratory tests will be performed to ensure the safety of the participants but will not be an assessment of the safety of the study drug.

8.3 Physical Examination

Physical examinations, including body weight, will be conducted at timepoints described in Table 1 and Table 2. Body weight will be measured in underwear and without shoes.

Any clinically significant physical examination findings (abnormalities) observed during the study will be reported as AEs. Any physical examination findings (abnormalities) persisting at the end of the study will be followed by the Investigator until resolution or until reaching a clinically stable endpoint.

8.4 Local Tolerability

Assessment of local tolerability will be conducted as presented in the schedule of assessments (Table 1 and Table 2) and as described in this section.

After each triptorelin injection, the injection site will be examined, at injection and 2 hours post injection, by a physician or medical research associate and assessed for characteristics such as but not limited to tenderness, redness, bruising, erythema, swelling, rash, pain, itching, induration, haematoma, ulceration or necrosis. If present, the extent of erythema, haematoma, rash, ulceration or necrosis will be described and assessed quantitatively; this will at least include measurement of maximum length and maximum width.

Any reaction deemed clinically significant by the Investigator meets the definition of a TEAE, thus it needs to be reported in the eCRF as such, as indicated in Section 8.1.2.6.

8.5 Vital Signs

Blood pressure and heart rate will be assessed at timepoints described in [Table 1](#) and [Table 2](#) with an automated device so that measurements are independent of the observer. Blood pressure and heart rate will be recorded in sitting position after 5 minutes of rest (seated). Absolute values and change from baseline will be analysed.

9 ASSESSMENTS OF PHARMACOKINETICS/PHARMACODYNAMICS

9.1 Pharmacokinetics

Sparse PK samples (triptorelin), will be taken in all participants as described in [Table 1](#).

9.1.1 *Sample Collection*

Blood samples for the assay of triptorelin will be collected in Vacutainer tubes at the timepoints indicated in [Table 1](#). Full details of sample collection, processing, required labelling, storage and the shipment process for these samples will be documented in the Study Manual.

On predetermined dates, samples will be shipped to the bioanalytical CRO under frozen conditions. For security reasons, aliquots of each sample will be shipped separately. The batch containing the second aliquot will not be shipped until the first one has arrived. Upon receipt at the bioanalytical CRO, samples will be checked and stored until analysis.

9.1.2 *Analytical Procedures*

The concentration of triptorelin will be analysed using a validated specific and sensitive method, and in accordance with Good Laboratory Practice (GLP). All details of sample collection, handling, shipment, methodology and reference ranges will be provided in the Study Manual and archived in the Trial Master File.

9.1.3 *Data Analysis*

Individual listings and summary statistics will be presented for PK concentrations.

9.2 Pharmacodynamics

Not applicable.

10 EXPLORATORY BIOMARKERS AND BIOBANKING

There are no exploratory biomarkers or biobanking planned for this study.

Note that a description of primary and secondary efficacy biomarkers can be found in Section [3.2](#).

11 STATISTICS

Detailed methodology for summary and statistical analyses of the data collected in this study will be documented in a statistical analysis plan (SAP), to be approved before the first participant enters the study. The SAP may include changes to the plans outlined in this protocol; however, any major modifications of the primary endpoint and/or its analysis will also be reflected in a protocol amendment.

Statistical evaluation will be performed using Statistical Analysis System (SAS[®]) Version 9.4 (or higher if available).

11.1 Analysis Populations

The following populations will be used during statistical analyses:

- **Screened population:** All participants screened (i.e. who signed the informed consent)
- **Safety population:** All participants who received at least one dose of study medication and have at least one post-baseline safety assessment
- **Intention-To-Treat population (ITT):** All participants who received at least one dose of study medication
- **Modified Intention-To-Treat population (mITT):** All treated participants having at least one baseline and at Month 3 post-baseline assessment of the primary efficacy endpoint
- **Per protocol (PP) set:** All participants in the mITT after exclusion of the participants who had major protocol deviations that could potentially affect the primary efficacy endpoint outcome for the participants
- **PK set:** All participants who received at least one dose of study medication and have at least one valid and quantifiable concentration.

11.1.1 *Populations Analysed*

Main phase

The primary efficacy analysis will be performed on the mITT population. Supportive analysis of the primary efficacy endpoints will be based on the ITT and the PP populations.

The secondary efficacy analyses will be based on the mITT population. Supportive analysis of the secondary analyses may be performed on the PP population.

The analyses of safety data will be performed based on the Safety population.

The analyses of PK data will be performed based on the PK population.

Extension phase

The analysis sets for the efficacy endpoints will be the ITT set and the PP set. Analyses and summary tables for the safety endpoints will be based upon the Safety population.

11.1.2 *Reasons for Exclusion from the Analyses*

Any major protocol deviation (see Section 13.1.2 for definition) will be described and listed and its impact on the inclusion of any participant in each analysis population will be specified. The final list of protocol deviations impacting each analysis population will be reviewed prior to database lock. The list may be updated, up to the point of database lock, to include any additional protocol deviations which may impact the analysis of each population.

11.2 Sample Size Determination

Main phase

The purpose of this study is to observe whether the effectiveness of triptorelin 3-month formulation in Chinese population of CPP children has the same or similar trend with that in

overseas CPP population, mainly using descriptive statistical analysis. Although no formal statistical testing will be carried out, the following assumptions were made, based on global pivotal study 2-54-52014-143 [[Zenaty 2016](#)], for the sample size to enable an evaluation of the trend of effectiveness:

- Expected outcome for the proportion of children with a suppressed LH response to the GnRH stimulation test (stimulated peak LH ≤ 3 IU/L) at Month 3 is 90%
- Null proportion is 70%
- An exact binomial test of a proportion with a one-sided nominal significance level of 0.05 and power =85%
- Expected common dropout rate =10%.

Under these assumptions, approximately 32 (28 with additional 10% dropouts) participants (Power Analysis and Sample Size (PASS) software) including three boys are planned to be enrolled into the study in order to observe the efficacy of the triptorelin 3-month formulation in the proportion of children with a suppressed LH response to the GnRH stimulation test at Month 3.

Extension phase

The number of participants included in the extension study will be dependent on the number of participants from study D-CN-52014-243 who give consent to continue into the extension study. A maximum of 32 participants will be expected to be enrolled in the extension phase.

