Diphereline® (international non-proprietary name (INN): triptorelin) is a synthetic GnRH analogue that is mainly characterised by the replacement of the L-glycine in the 6th position by a D-tryptophan. This structural modification increases both the resistance to enzymatic degradation and the affinity to the pituitary receptor, thus prolonging the plasma half-life ($t_{1/2}$) and increasing the potency of the drug.

In China, Diphereline® is available as a 1-month formulation, which is approved for use in patients with prostate cancer, CPP, endometriosis, fibromyomas and female infertility, and a 3-month formulation (containing 15 mg of triptorelin pamoate to ensure the release of 11.25 mg of product), which is approved for prostate cancer.

Several studies have assessed the efficacy and safety of triptorelin 3-month PR release formulation, including three Ipsen-sponsored phase III studies and two independent studies [\[Carel 2006, Martinez-Aguayo 2006, Zenaty 2016\]](#). In 2017, Durand et al. [\[Durand 2017\]](#) performed a meta-analysis to assess the data available from a total of 153 children with CPP (13 boys and 140 girls) that had participated in the clinical studies and received treatment with this triptorelin formulation. Across all studies, the primary outcome was the proportion of children with suppressed LH response (peak LH ≤ 3 IU/L) to the GnRH test 3 months after triptorelin injection. Secondary outcomes included the proportion of children with suppressed peak LH response at 6 months, and the proportion of children with suppressed peak FSH response (≤ 3 IU/L), proportion of girls with suppressed oestradiol (≤ 20 pmol/L) and proportion of boys with suppressed testosterone (≤ 30 ng/dL) at 3 months [\[Durand 2017\]](#). The authors concluded that the 3-month formulation of triptorelin was efficacious in suppressing LH peak and other gonadal hormones and in slowing the progression of CPP in children.

The worldwide marketing status of all triptorelin formulations of which Ipsen is the marketing authorisation holder (MAH) can be found in the Investigator's Brochure (IB). Further details/additional information regarding risks and benefits to participants may also be found in the IB.

A more detailed description of the product is provided in Section 3.7 and Section 6. Further details on administration procedures and dosage are provided in Section 6.2.

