2.3 Study Hypothesis

The study hypothesis is that the effectiveness of triptorelin 3-month formulation in Chinese population of CPP children has the same or similar trend with that in overseas CPP population.

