11.3 Significance Testing and Estimations

The observed response rate in global study 2-54-52014-143 was 83.8% (95% CI: 68.0% to 93.8%). With N=28, there is 90% probability that the observed response rate will be within 16 percentage points of the true response rate based on a simulation. Due to the small sample size and potential wider precision of the estimator, the primary endpoint will be summarised descriptively. No formal hypothesis test will be performed.

For the primary efficacy endpoint, the summary statistics of number and percentage of participants and the exact two-sided 90% confidence interval (CI) for a binomial proportion will be computed by SAS® using the exact binomial distributions on the mITT (primary population of analysis), ITT and PP.

For secondary efficacy endpoints related to a change at Month 3 and Month 6 compared to baseline, the descriptive summary statistics (n, mean, SD, median, minimum, maximum) will be calculated on the mITT. In addition, secondary efficacy endpoints may be performed on the PP. Exact two-sided 90% CIs will also be constructed for all secondary endpoints expressed as percentages.

For extension phase efficacy endpoints related to a change at Month 9 and Month 12 compared to baseline, the descriptive summary statistics (n, mean, SD, median, minimum, maximum) will be calculated on the ITT and PP. Exact two-sided 90% CIs will also be constructed for all extension phase efficacy endpoints expressed as percentages.

The analysis results based on the statistical methods above will provide the reference for whether the efficacy of treatment of CPP in children in China has same or similar trend with that in overseas CPP population.

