**2.6 Change from Statistical Section of the Protocol**

There is no change in SAP from statistical section of the protocol.

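### The 90% Month 3 suppression rate behind the 85% power is attributed to study 2-54-52014-143, for which the protocol itself reports 83.8%

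*Protocol*

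**What the plan says.** Protocol 11.2 says that "the following assumptions were made, based on global pivotal study 2-54-52014-143". The list that follows has an expected proportion suppressed "at Month 3 is 90"%, a null proportion of 70%, "An exact binomial test of a proportion with a one-sided nominal significance level of 0.05 and power =85"%, and 10% dropout. These lead to 28 evaluable and 32 enrolled children. The synopsis and SAP 2.3 give the same inputs and the same source.

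Protocol 11.3 then opens with: "The observed response rate in global study 2-54-52014-143 was 83.8% (95% CI: 68.0% to 93.8"%). It adds that with N=28 "there is 90% probability that the observed response rate will be within 16 percentage points of the true response rate", and says that the primary endpoint will be summarised descriptively with no formal hypothesis test. SAP 5.7.1.1 also rules out formal testing.

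The 83.8% appears only in Protocol 11.3. It is not in the synopsis or the SAP, and no section says why 90% was chosen for planning.

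**The concern.** The protocol associates two rates with one earlier study, 90% and 83.8%, and does not say how it gets from one to the other. Someone who reads only the synopsis or the SAP sees 90% credited to study 2-54-52014-143 and would reasonably take it for what that study found.

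The power statement is the stated reason for 28 evaluable children, and it depends heavily on this input. The gap between 70% and 90% is 20 percentage points; the gap between 70% and 83.8% is 13.8. If the earlier study's own estimate is used, the quoted 85% does not hold.

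The documents also frame the trial as showing whether efficacy in Chinese children "has the same or similar trend with that in overseas CPP population". A reader making that comparison should be able to tell which overseas rate was observed and which was assumed.

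**Working it through.** **Inputs.** From Protocol 11.2: p0 = 0.70, p1 = 0.90, one-sided alpha 0.05, exact binomial test, n = 28 evaluable, 10% dropout. From Protocol 11.3: observed rate 0.838, 95% CI 0.680 to 0.938.

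**1. Reproduce the plan's figures.** The nominal rule is the smallest c with P(X ≥ c | n = 28, p = 0.70) ≤ 0.05.
- c = 23 gives 0.113, which is too large.
- c = 24 gives 0.0474, so the rule is at least 24 of 28.

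Power at 90% is P(X ≥ 24 | 28, 0.90) = 0.858. Enrolment is 28 / (1 − 0.10) = 31.1, rounded up to 32. The stated power and both sample sizes are correct on their inputs.

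**2. Change only the true rate.** Power = P(X ≥ 24 | 28, p):

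| True rate p | Where it comes from | Power |
|---|---|---|
| 0.90 | planning value, 11.2 | 85.8% |
| 0.838 | observed rate, 11.3 | 51.6% |
| 0.680 | lower 95% limit, 11.3 | 2.9% |
| 0.938 | upper 95% limit, 11.3 | 97.3% |

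Power equals 85% at p = 0.898, so the claim needs a true rate of about 90%.

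**3. Does the number evaluable matter?** For every n from 24 to 32, with the rule recalculated each time, power is 72% to 86% at a true 90% and 34% to 52% at 83.8%. Both maxima occur at n = 28, so the comparison above uses the sample size most favourable to the plan.

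**4. Is 90% compatible with the earlier study?** Among all counts x/n with n from 10 to 199 that round to 83.8%, only 31/37 has an exact (Clopper-Pearson) 95% interval of 68.0% to 93.8% (67.99% to 93.81%). This count is back-calculated; the documents do not state it. If the true rate were 90%, P(X ≤ 31 | 37, 0.90) = 0.16. So 90% is not ruled out, but it is more optimistic than the estimate. The same interval also contains the 70% null.

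**5. Does the precision statement in 11.3 depend on the 90%?** For Binomial(28, p), the probability that x/28 falls within 0.16 of p is 0.983 at p = 0.838 and 0.995 at p = 0.90. The statement of 90% probability is met at both rates.

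**6. Are the two rates on the same endpoint?** Protocol 11.3 gives no visit or LH cut-off for the 83.8%. Protocol 1.1 describes a meta-analysis of the earlier 3-month triptorelin studies, cites the publication of study 2-54-52014-143 among them, and gives their common primary outcome as the "proportion of children with suppressed LH response (peak LH ≤ 3 IU/L) to the GnRH test 3 months after triptorelin injection". The 83.8% also opens the section on estimating the Month 3 primary endpoint. A match is therefore likely, but it is an inference.

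**The case against.** The strongest reply is that an expected rate and an observed rate may differ without contradiction. Protocol 11.2 calls 90% an expected outcome, 11.3 calls 83.8% an observed one, and 90% lies inside the reported interval. The phrase about the earlier study introduces a list that also contains the significance level and the power, which no earlier study could supply, so it may have been meant loosely. This stands in part: 90% is a defensible planning value. But being compatible with a study is not the same as being taken from it, and a rate, unlike a significance level, is something a reader expects to find in the named source.

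The second reply is that nothing inferential depends on it. There is no test and no success rule against 70%, and N=28 has a second justification, the precision statement, which holds at either rate. This is correct and limits the point to the stated power and its justification. The 51.6% is a planning sensitivity figure and not a chance that the trial fails; a true rate of 83.8% would match the overseas result.

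Third, the 83.8% is printed in the very next subsection of the protocol, and the power is openly conditional on the listed 90%. That is also true, but the figure is missing from the synopsis and the SAP and is nowhere reconciled with the 90%.

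Finally, the 83.8% might refer to another visit, cut-off or analysis set. The documents cannot exclude this. If it does, the attribution still needs a sentence to say so.

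**Conclusion.** The concern holds and is minor. The sizing rate of 90% is credited to a study for which the protocol reports 83.8%, and the documents do not explain the difference. The quoted 85% power is correct only for a true rate of about 90%; at the rate reported for the named source it is about 52%.

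This rests on 28 evaluable children, the nominal exact one-sided 5% test in Protocol 11.2, and the inference that 83.8% is the Month 3 rate of peak LH ≤ 3 IU/L. The effect is confined to the power statement and its attribution. The primary analysis, the confidence interval and the comparison with the overseas population are unaffected.

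**What to change.** Keep N=32. In the synopsis, Protocol 11.2 and SAP 2.3:

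1. Name the actual source or reasoning for 90%, or stop attributing it to study 2-54-52014-143.
2. Restate the nominal power at both rates, for example: *With 28 evaluable children, a nominal one-sided 5% exact test against 70% (at least 24 responders) would have about 86% power if the true rate is 90%, and about 52% if it is the 83.8% observed in study 2-54-52014-143. These figures describe the planning assumptions only; no test is planned and 24 responders is not a success criterion.*

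The last clause keeps readers from taking the 52% as a chance of failure. While the text is open, adding the visit, cut-off and count behind the 83.8% to Protocol 11.3 would settle the endpoint question, though the correction does not depend on it.

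The cost is one or two sentences in each place. No extra children are needed, and the endpoint, analysis and outputs do not change. The only drawback is a less favourable-looking power statement.

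### The stated 85% power is right at 28 evaluable children but 28 is a saw-tooth peak, so 32 enrolled gives about 81% on average under random 10% dropout and 79% with none

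*Protocol*

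**What the plan says.** Protocol 11.2 sets out the sizing assumptions, and the synopsis and SAP 2.3 repeat them. The expected proportion is given as "stimulated peak LH ≤ 3 IU/L) at Month 3 is 90" per cent, and the reference as "Null proportion is 70" per cent. The method is "An exact binomial test of a proportion with a one-sided nominal significance level of 0.05 and power =85" per cent. Loss is covered by "Expected common dropout rate =10" per cent. The result is "approximately 32 (28 with additional 10% dropouts) participants".

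The primary analysis is on the mITT, which Protocol 11.1 defines as "All treated participants having at least one baseline and at Month 3 post-baseline assessment of the primary efficacy endpoint". The evaluable number is therefore the number of treated children with a Month 3 result.

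Protocol 11.3 says "No formal hypothesis test will be performed". The result will be a percentage with an exact two-sided 90% confidence interval. The same section adds a precision statement for N=28: a 90% probability that the observed rate falls within 16 percentage points of the true rate.

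Neither document gives the critical count, the attained significance level, or the power at any number other than the design number.

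**The concern.** Inflating a sample size for dropout normally treats the evaluable target as a minimum: if fewer children leave than expected, power should rise. An exact binomial test need not behave that way. Its critical count moves in whole steps, so power rises and falls as n grows. If the target sits on a peak, keeping more children than planned lowers the power, and losing one below the target lowers it sharply.

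A reader who sees 85% beside an enrolment of about 32 will take it as a property of the planned study. It is also the figure that justifies the study's size. No test is planned, but the reported interval behaves in the same way: its lower limit is above 70% exactly when the test would reject. The 85% is thus in effect the chance that the published interval clears the plan's own 70% reference.

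**Working it through.** **Inputs.** Expected rate 0.90, null rate 0.70, one-sided level 0.05, dropout 10%, 28 evaluable and 32 enrolled (all Protocol 11.2). Evaluable means in the mITT (Protocol 11.1).

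**Formulas.** For n evaluable children, the critical count c is the smallest integer with P(X ≥ c | n, 0.70) ≤ 0.05. Power is P(X ≥ c | n, 0.90), with X binomial.

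**The plan's own figure.** At n = 28, c = 24. The attained level is P(X ≥ 24 | 28, 0.70) = 0.0474 and power is P(X ≥ 24 | 28, 0.90) = 0.858. Inflation: 28 / (1 − 0.10) = 31.1, rounded up to 32. Both stated figures reproduce.

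**Other evaluable numbers.**

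| Evaluable n | Count needed | Attained level | Power at 90% | Exact 90% CI lower limit at that count |
|---|---|---|---|---|
| 27 | 24 | 0.0202 | 71.8% | 73.7% |
| 28 | 24 | 0.0474 | 85.8% | 70.2% |
| 29 | 25 | 0.0379 | 84.2% | 71.2% |
| 30 | 26 | 0.0302 | 82.5% | 72.0% |
| 31 | 27 | 0.0239 | 80.7% | 72.9% |
| 32 | 28 | 0.0189 | 78.9% | 73.6% |
| 33 | 28 | 0.0414 | 89.4% | 70.7% |

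From 20 to 32, only n = 28 reaches 85%. The next is 33, one more than the planned enrolment.

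**Link to the interval.** The lower limit of the exact two-sided 90% interval is the rate p that solves P(X ≥ x | n, p) = 0.05. It exceeds 70% exactly when P(X ≥ x | n, 0.70) < 0.05, which is the rejection rule. For example, 24/28 gives 70.2% and clears 70%; 27/32 gives 69.9% and does not; 28/32 gives 73.6%.

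**Dropout taken as exactly 10%.** 32 × 0.90 = 28.8, so 28 or 29 children remain and power is 85.8% or 84.2%.

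**Dropout taken as random.** Assume each of 32 children is evaluable independently with probability 0.90.
- P(exactly 28) = 18.8%, P(more than 28) = 60.0%, P(fewer than 28) = 21.1%. P(28 or 29) = 42.2%.
- Average power is the sum over n of P(N = n) × power(n). Evaluable numbers 28 to 32 contribute 0.657, 27 contributes 0.084, and 26 or fewer contribute 0.070. The total is 0.811.
- Under the same model with other rates, the average is 81.4% at 5% dropout and 78.3% at 15%. With no dropout it is the n = 32 value, 78.9%.

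**The case against.** The strongest reply is that nothing in the plan is miscalculated. Design power is conventionally quoted at the target evaluable number, the wording links 28 to 32 through the dropout allowance, and the documents never claim 85% at 29 to 32. At exactly the planned loss the power is 85.8% or 84.2%. This stands, and it rules out reading the 85% as an arithmetic error.

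A second reply is that the fall from 28 to 32 comes from discreteness. The attained level drops from 0.0474 to 0.0189 over that range. At 32, a cutoff of 27 would have a level of 0.0510 and power of 90.6%, so it misses the 0.05 limit by about 0.001. A reader might infer that extra children do harm, or that enrolment should change. The documents do not support that: the planned analysis is estimation, and the expected width of the exact 90% interval at a true rate of 90% narrows from 21.1 points at 28 to 19.6 points at 32.

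A third reply is that no decision depends on 70%. Both documents exclude formal testing, and 70% appears only as a sizing assumption. This also stands and limits the consequence. It does not remove it, because the 85% is still offered as justification for the size and maps directly onto the reported interval.

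Two further inferences should be resisted. The 85% is not the plan's only operating characteristic, since Protocol 11.3 also gives the 16-point precision statement, again at N=28. Nor does the 85% extend to the ITT analysis with non-responder imputation. That is a sensitivity analysis (SAP 5.7.2.3), and the plan claims no power for it.

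**Conclusion.** The point holds as a minor clarification. The 85% is correct at the target of 28 evaluable children and nearly so at 29, but the planned enrolment of 32 does not reliably deliver it. The shortfall from 85% is about 4 points on average under random 10% dropout (81.1%) and about 6 points if all 32 are evaluable (78.9%). One child below the target costs 14 points (85.8% to 71.8%).

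These figures take the plan's 90% and 70% as given. The 81% also rests on independent dropout at 10%, which the plan does not specify, and on every dropout lacking a Month 3 result. The numbers at each fixed n need neither assumption. The design is not invalidated, and no analysis changes.

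**What to change.** Keep 32 children. In Protocol 11.2, the synopsis and SAP 2.3, replace the bare power figure with a statement along these lines:

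- Exact power at a true rate of 90% is about 86% at 28 evaluable children in the mITT, which meets the 85% target. It is about 84%, 82%, 81% and 79% at 29, 30, 31 and 32.
- It averages about 81% if dropout from 32 enrolled is random at 10%.
- Because no formal test is planned, the figure is the nominal probability that the lower limit of the exact two-sided 90% confidence interval exceeds 70%.

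Do not present the response counts behind these figures as a success rule, because the plan sets none. The cost is wording in three places: no extra children, no change to any analysis, and a slightly less favourable stated power.
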